6.6 Dose Modification and Toxicity Management

AZD0466 may be withheld and the dose reduced due to haematological or non-haematological toxicities. In general, no AZD0466 dose modification is required if a patient experiences a Grade 1 or Grade 2 AE. However, AZD0466 should be modified or discontinued when the AEs described in this section are observed whether during ramp-up or once target dose is reached. Modifications based on cardiac AEs are described in Section 6.6.5.

Acceptable dose modifications shown in Table 4 are applicable during ramp-up and once target dose is reached. A maximum of 3 dose modifications are acceptable, except for CTCAE Grade 3 or 4 haemorrhage and any intracranial haemorrhage or haematoma, of which only one event is allowed. Also see Table 5, Table 6, Table 7, and Table 8.

Table 4 Dose Reduction Modifications

Cohort level	AZD0466 dose	Dose reductions		
		1 lower dose	2 lower doses	3 lower doses
DL-1	37.5 mg	--	--	--
	75 mg	37.5 mg	--	--
	150 mg	75 mg	37.5 mg	--
DL1	75 mg	37.5 mg	--	--
	150 mg	75 mg	37.5 mg	--
	300 mg	150 mg	75 mg	37.5 mg
DL2	150 mg	75 mg	37.5 mg	--
	300 mg	150 mg	75 mg	37.5 mg
	600mg	300 mg	150 mg	75 mg
DL3	300 mg	150 mg	75 mg	37.5 mg
	600 mg	300 mg	150 mg	75 mg
	1200 mg	600 mg	300 mg	150 mg
DL4	600 mg	300 mg	150 mg	75 mg
	1200 mg	600 mg	300 mg	150 mg
	2400 mg	1200 mg	600 mg	300 mg
DL5 ^a	1200 mg	600 mg	300 mg	150 mg
	2400 mg	1200 mg	600 mg	300 mg
	3600 mg	2400 mg	1200 mg	600 mg
DL6 ^a	2400 mg	1200 mg	600 mg	300 mg
	3600 mg	2400 mg	1200 mg	600 mg
	5400 mg	3600 mg	2400 mg	1200 mg
DL6 – alternative ramp-up ^b	1400 mg	600 mg	300 mg	150 mg
	2800 mg	1200 mg	600 mg	300 mg
	5400 mg	3600 mg	2400 mg	1200 mg

^a AZD0466 doses shown are illustrative. Actual doses will not exceed a 2-fold increase of a dose declared tolerable by the SRC, or the maximum feasible dose as specified in Section 11.4.7.5.

^b SRC to determine ramp-up as well as target dose.

DL, dose level; SRC, Safety Review Committee

While on study, patients diagnosed with COVID-19 and are thought to be receiving clinical benefit as deemed by the investigator may continue to receive AZD0466; however, must pause treatment if they meet pause or discontinuation criteria for dose modifications based on haematological parameters (Section 6.6.1, neutropenia), or CTCAE Grade 2 or higher non-haematological toxicities (Section 6.6.3), which would include pneumonia or other infectious complications.

6.6.1 Dose Modifications Based on Haematological Parameters

Myelosuppression and cytopenias are expected outcomes of leukaemia treatment, hence the aim of these dose modification guidelines is to prevent cumulative bone marrow suppression. Dose modifications for haematological changes are not allowed in the first 35 days after starting AZD0466 during Cycle 1 but supportive care should be provided as clinically indicated.

If a patient experiences a clinically significant and/or **unacceptable haematological toxicity** (including a DLT) considered by the Investigator to be related to study treatment and not attributable to the disease (or to disease-related processes) under investigation, dosing in subsequent cycles will be withheld and may subsequently be restarted at **one lower dose** (equivalent to one dose reduction; [Figure 3](#)) and supportive therapy ([Appendix F](#)) administered as required. Recommended dose modifications for haematological toxicities associated with AZD0466 observed in patients with haematological malignancies are shown in [Table 5](#).

Table 5 Recommended Dose Modifications for Haematological Toxicities

Toxicity Grade	Occurrence	Action
Grade 4 neutropenia, with or without fever or infection	Occurrence prior to achieving remission	Administer prophylactic or treatment anti-infectives and growth factor support as clinically indicated. In most instances, AZD0466 should not be interrupted due to neutropenias prior to achieving remission; however, Investigator judgment may be applied to determine the aetiology of neutropenias.
	Occurrences after achieving remission and lasting at least 7 days	Withhold AZD0466 until infection is resolved, and antibiotics no longer required (except prophylactic) and ANC $\geq 0.5 \times 10^9/L$. ^a Dosing should be discussed with Medical Monitor.
Presence of significant bleeding events with or without thrombocytopenia, such as: 
• Grade 3 or 4 haemorrhage• Any grade serious haemorrhage event• Any grade intracranial haemorrhage or haematoma	Any	Withhold AZD0466 Maintain platelets at $\geq 50 \times 10^9/L$ until resolution of bleeding. Following discussion with Medical Monitor, if evidence of clinical benefit, may consider re-challenge at 2 dose levels below current dose.

Table 5 Recommended Dose Modifications for Haematological Toxicities

Toxicity Grade	Occurrence	Action
For any other bleeding events eg, petechiae, purpura, bleeding gums, epistaxis, etc	Any	Monitor platelets and action as above if thrombocytopenia \geq Grade 3

^a Recovery of ANC to $\geq 0.5 \times 10^9/L$ only applicable for patients with ANC $\geq 0.5 \times 10^9/L$ at baseline/screening. For other patients discuss with Medical Monitor.

ANC, absolute neutrophil count.

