6.6.2 Retreatment Criteria

Administration of AZD0466 in subsequent cycles will be guided by presence of measurable disease and adequate haematopoiesis, as described below.

Criteria for holding administration of AZD0466

The haematological criteria for withholding AZD0466 are as follows (Table 6):

- 1 **Inadequate haematopoiesis** as demonstrated by lack of peripheral blood count recovery [absolute neutrophil count (ANC) $< 0.5 \times 10^9/L$, and platelet count $< 50 \times 10^9/L$] in the absence of active bone marrow leukaemia (marrow blasts $< 5\%$).
 - Some patients with low blood counts (ANC $< 0.5 \times 10^9/L$ and platelet count $< 50 \times 10^9/L$) may have an aplastic or hypoplastic marrow ($< 10\%$ cellularity on bone marrow core biopsy). In patients with an aplastic or hypoplastic marrow and high leukaemic burden (eg, 5% cellularity and 95% leukaemic blasts), or if the Investigator determines the hypocellularity is attributable to residual leukaemia and not AZD0466, continued administration of AZD0466 may be permitted after discussion with the Medical Monitor.
 - If AZD0466 is withheld due to cytopenias and bone marrow aplasia/hypoplasia ($< 10\%$ cellularity on core bone marrow core biopsy) in the absence of leukaemia (eg, 5% leukaemic blasts), the patient should be closely monitored for blood count recovery and a repeat bone marrow assessment should be considered at weekly intervals.
- 2 **Progressive disease** (Appendix J and Appendix K): permanently discontinue AZD0466 in the absence of clinical benefit after discussion with the Medical Monitor.

Criteria for administration/continuation of AZD0466

The next cycle of AZD0466 can proceed without delay if ANC $> 0.5 \times 10^9/L$ and platelets $> 50 \times 10^9/L$ (without platelet or growth factor support). For patients without peripheral blood count recovery, the next cycle can start if there is active leukaemia with 5% or higher blasts in the bone marrow.

Table 6 Treatment Criteria Based on Bone Marrow, ANC and Transfusion Independent Platelet Count in the Absence of Peripheral Blasts

Event	ANC ($10^9/L$)	Platelets ($10^9/L$)	Bone marrow	Action
Cycle 1	> 0.5	> 50	-	
 Evaluate bone marrow disease but continue to next cycle irrespective of percentage of blasts (unless determined to have rapidly progressive disease and taken off study)

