	< 0.5	< 50	< 5% blast and cellularity < 10%	
 No count recovery at day 35 hold AZD0466 wait to see if recovery at Day 42. If no recovery, repeat bone marrow at Day 42. Blasts count < 5% and no count recovery this is prolonged myelosuppression and a DLT. Discontinue AZD0466 Blasts count \geq 5% and no count recovery, either continue to Cycle 2 or discontinue due to lack of response after discussion with Medical Monitor
	< 0.5	< 50	> 5% blast	
 If significant reduction of leukaemic burden and clinical benefit as assessed by the Investigator, discuss with the Medical Monitor and may continue to Cycle 2. If lack of clinical response or benefit consider discontinuation from study.
Cycle 2 and beyond	> 0.5	> 50	< 5% blast and normal cellularity (> 10 %)	
 Continue to next cycle
			<5% blast and bone marrow hypocellular (< 10% cellularity)	
 Hold AZD0466 and monitor for count recovery and assess bone marrow weekly. Once adequate hemopoiesis met (> 20% cellularity) restart AZ0466. Consider restarting at one lower dose than the current dose.
	> 0.5	> 50	> 5% blast	
 Continue to next cycle if the patient is deriving benefit in the opinion of the Investigator
	< 0.5	< 50	Aplastic/ Hypoplastic (< 10% cellularity) and < 5% blasts	
 Hold and monitor for count recovery and assess bone marrow weekly. Once adequate hemopoiesis met (> 10% cellularity), restart AZ0466. Consider restarting at one lower dose than the current dose. If hypocellularity is due to high leukaemic burden (95% blast) or if Investigator attributes hypocellularity to residual leukaemia, consider dosing after discussion with Medical Monitor

Table 6 Treatment Criteria Based on Bone Marrow, ANC and Transfusion Independent Platelet Count in the Absence of Peripheral Blasts

Event	ANC ($10^9/L$)	Platelets ($10^9/L$)	Bone marrow	Action
	< 0.5	< 50	> 5% blast	
 Discuss with Medical Monitor consider discontinuation due to continued lack of response. Further cycles may be considered

ANC, absolute neutrophil count; DLT, dose-limiting toxicity.

Contact the Medical Monitor to discuss action with AZD0466 for any scenario not described above.

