Severe (≥ 7.0 mmol/L) or symptomatic	As above, plus Calcium gluconate ^a 100 to 200 mg/kg by slow IV infusion if concurrent ECG changes (including life-threatening arrhythmias) Regular IV insulin and dextrose, monitor blood glucose closely Consider sodium bicarbonate ^a if patient is acidotic Consider albuterol (to be avoided in patients with acute coronary disease) Dialysis may be required
Renal dysfunction (uraemia)	Fluid and electrolyte management Uric acid and phosphate management Adjust doses of renally excreted medication Dialysis or haemofiltration may be required

^a Sodium bicarbonate and calcium gluconate should not be administered through the same line.

Recommended management adapted from [University of Texas MD Anderson Cancer Center 2018](#), and [Coiffier et al 2008](#). ECG, electrocardiogram; IV, intravenous.

Laboratory parameters indicating TLS (including blood urea nitrogen, creatinine, phosphate/phosphorus, uric acid, calcium, potassium, and lactate dehydrogenase [LDH]) will be evaluated. Fluid balance must be monitored per institutional standards. If more aggressive hydration management is indicated, patient hospitalisation will be considered at Investigator discretion. Allopurinol prophylaxis should be considered based on institutional guidelines.

F 1.4 Reporting Adverse Events of TLS

The Investigator will report TLS as an adverse event or serious adverse event of "laboratory

"TLS" or "clinical TLS" according to the classification of TLS in Appendix [G 1](#). For the purposes of adverse event reporting, a CTCAE grade for TLS should also be recorded, as follows:

- CTCAE Grade 3: TLS present
- CTCAE Grade 4: TLS with life-threatening consequences; urgent intervention indicated
- CTCAE Grade 5: Death

TLS will also be graded according to Cairo-Bishop criteria for the purposes of dose-limiting toxicity assessment and summary of adverse events of special interest (Appendix [G 2](#); [Cairo and Bishop 2004](#)).

F 2 Guidance for Management of haematological changes

F 2.1 Thrombocytopenia and Haemorrhage

Platelet transfusions are permitted as per institutional standards. However, due to the mechanism of action of AZD0466, platelet transfusion may have limited efficacy within 24 to 48 hours after AZD0466 infusion.

AZD0466 should be withheld in presence of significant bleeding events with or without thrombocytopenia, such as:

- Grade 3 or 4 haemorrhage
- Any grade serious haemorrhage event

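### Protocol Sections 6.6.1 and 6.6.2 give conflicting haematological hold instructions: the 35-day bar against the bleeding hold, and the proceed and restart rules against individual rows of Table 6

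*Protocol*

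**What the plan says.** **Cycle 1 and bleeding.** The opening text of protocol Section 6.6.1 says "Dose modifications for haematological changes are not allowed in the first 35 days after starting AZD0466 during Cycle 1" and offers supportive care instead. For unacceptable haematological toxicity it then says "dosing in subsequent cycles will be withheld and may subsequently be restarted at" one lower dose. Table 5, in the same section, lists recommended dose modifications for haematological toxicities. One row covers significant bleeding: Grade 3 or 4, serious, or any intracranial bleed. Its occurrence column reads Any and its action is to withhold; after discussion with the Medical Monitor the site "may consider re-challenge at 2 dose levels below current dose". The next row sends lesser bleeding to the same action when thrombocytopenia is Grade 3 or worse.

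Section 6.6, which governs all of these tables, says "AZD0466 should be modified or discontinued when the AEs described in this section are observed whether during ramp-up or once target dose is reached". Appendix F 2.1 says "AZD0466 should be withheld in presence of significant bleeding events with or without thrombocytopenia, such as", followed by the same three kinds of bleed.

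**Starting the next cycle.** In Section 6.6.2 the sentence opening "The next cycle of AZD0466 can proceed without delay if ANC" sets limits of 0.5 ×10⁹/L for ANC and 50 ×10⁹/L for platelets, without platelet or growth factor support. It sets no marrow condition. Table 6, for Cycle 2 and beyond, has a row for blasts below 5% with cellularity below 10%, and its action is to hold.

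**Restarting after a hold.** That row ends "Once adequate hemopoiesis met (> 20% cellularity) restart AZ0466". The row for low counts with a hypoplastic marrow ends "Once adequate hemopoiesis met (> 10% cellularity), restart AZ0466".

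**The concern.** These are safety instructions, and Section 8 tells sites that waivers are not allowed and that adherence is essential. Where two current passages direct different actions for the same patient, a site departs from one of them whatever it does.

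Two consequences follow for the analysis. First, SAP Section 4.6.2.1 (Deviation 4) counts treatment administration that was not according to protocol, and considered to have a potential effect on study outcomes, as an important deviation. That cannot be judged consistently if the protocol states two rules. Second, under Section 11.4.7.1 a patient without a DLT is DLT-evaluable only with at least three doses at target between Day 8 and Day 29. Holds in Cycle 1 can therefore, in some cases, decide who enters the mTPI-2 counts.

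**Working it through.** No sample size, power or event figure is involved. The check is a comparison of the passages, plus one count for evaluability.

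**1. Does the 35-day bar overlap the bleeding hold?**
- Section 11.4.1: Module 1 Cycle 1 lasts 35 days, made up of a 7-day ramp-up and 28 days at target. Ramp-up therefore lies wholly inside the bar.
- Module 1 infusions in that window fall on Days 1, 4, 8, 15, 22 and 29, which is six. This count is for Module 1 only. Module 2 Cycle 1 lasts 21 days, with infusions on Days 1, 4, 8 and 15 (Section 12.1.5).
- Take a significant bleed on Day 10. The Section 6.6.1 text gives no modification. Table 5 and Appendix F 2.1 give withhold, and Section 6.6 confirms that the section's actions apply this early. Table 5 files bleeding under haematological toxicities and lists withholding among dose modifications, so nothing written takes the event outside the bar.

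**2. Does the proceed rule conflict with Table 6?**
- Cycle 1: the Table 6 row for recovered counts continues to the next cycle whatever the blast percentage, unless disease is rapidly progressive. No conflict.
- Cycle 2 and beyond, recovered counts, blasts below 5%, cellularity above 10%: continue. No conflict.
- Cycle 2 and beyond, recovered counts, blasts above 5%: continue if the Investigator sees benefit. This adds a condition but does not order a hold.
- Cycle 2 and beyond, blasts below 5%, cellularity below 10%: hold. The ANC and platelet cells of this row are blank in the extracted text. A separate row below it covers the same marrow finding at ANC below 0.5 and platelets below 50, so the blank cells are most naturally read as continuing the block above (over 0.5 and over 50). On that reading the text says proceed and the table says hold.

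**3. Are the restart thresholds consistent?**

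| Place | Cellularity | Instruction |
|---|---|---|
| Table 6, first Cycle 2+ row | above 10%, called normal | continue |
| Table 6, hypocellular row (blank counts) | above 20% | restart |
| Table 6, low-count row | above 10% | restart |
| Section 6.6.2, hold criterion 1 | none stated | hold if ANC < 0.5, platelets < 50 and blasts < 5% |

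Consider a held patient at 15% cellularity with blasts below 5%. If counts are recovered, the first row says continue, but the restart threshold of the hypocellular row is not met. If both counts are low, the low-count row's restart threshold is met, but criterion 1 still says hold.

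**4. When does a Cycle 1 hold change DLT-evaluability?**
- Planned target doses fall on Days 8, 15, 22 and 29, so there are four. The requirement is three, and 3/4 = 75%.
- One missed: 4 − 1 = 3, still evaluable.
- Two missed: 4 − 2 = 2, and 2/4 = 50%, so not evaluable unless a DLT occurred.
- A re-challenge dose two levels lower is not a dose at target, so it counts as missed here.

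**The case against.** The best defence of Section 6.6.1 is context. The bar follows directly on a statement that cytopenias are expected and an aim of preventing cumulative marrow suppression, so haematological changes may mean cytopenias alone. Bleeding is handled separately: Table 5 applies with or without thrombocytopenia, Section 6.6 sets a special one-event limit for haemorrhage, and Appendix F 2.1 agrees with Table 5. This is a plausible account of the intent. It stands as an explanation but not as a resolution, because the limit to cytopenias is nowhere written.

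A reader might infer that a site would go on infusing after a major bleed. The documents do not support that. Section 7.1 requires discontinuation on Investigator decision or for any AE that contraindicates dosing, and Section 8 sends immediate safety concerns to the Medical Monitor at once. These provisions soften the consequence and leave the contradiction in place.

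On Table 6, the hold row tells sites to monitor for count recovery, and the row after it restates its counts instead of leaving them blank. Both sit awkwardly with the recovered-count reading, which is supported but not proven. The Section 6.6.2 sentence is also permissive, and the section opens by requiring adequate haematopoiesis, so the table row could be read as a specific qualification. The fallback of contacting the Medical Monitor does not settle it, since it covers only scenarios that the table does not describe.

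**Conclusion.** The conflict over Cycle 1 bleeding is firm: it lies in current operative text and needs no assumption about table layout. The conflict between proceed and hold is narrower. It is confined to Cycle 2 and beyond with blasts below 5% and cellularity below 10%, and it rests on reading the blank count cells as over 0.5 and over 50. The two restart values, a two-fold difference, are stated outright; which patients the higher one applies to depends on that same reading.

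Three stronger inferences go too far:
- Recovered counts do not in general mean both proceed and hold. Only one marrow category does so.
- A patient at 15% cellularity with low counts is not simply restarted ahead of one with recovered counts. Criterion 1 of Section 6.6.2 still holds the former if ANC, platelets and blasts are all below their limits. That is a further mismatch to resolve.
- A Cycle 1 hold does not by itself remove a patient from the DLT-evaluable set. That needs more than one of the four target doses missed and no DLT, and Section 11.4.7.1 lets such a patient be replaced.

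Nor is there a basis for claiming damage to response-duration results. SAP Section 1 records that the study was terminated and Part B not initiated, and SAP Section 8.10 keeps complete response and OS as the efficacy endpoints. What remains is conflicting safety instructions and inconsistent classification of dosing deviations.

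**What to change.** Reconcile the passages:
- In Section 6.6.1, state whether the 35-day bar covers the bleeding rows of Table 5, consistently with Section 6.6 and Appendix F 2.1.
- Make the proceed sentence of Section 6.6.2 and the hypocellular row of Table 6 agree, and fill in that row's count cells if they are blank in the source.
- Use one restart definition of adequate haemopoiesis across Table 6, and square the low-count row with hold criterion 1 of Section 6.6.2.

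Which action or value applies is a clinical decision for the sponsor. The cost is wording edits to Sections 6.6.1 and 6.6.2 and Table 6, with no added assessments. Since the study has been terminated, the practical uses are to record in the protocol deviation specification which reading was applied to Cycle 1 bleeding holds, and to correct the text before it is reused.

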6.5.1 Permitted Concomitant Medications and Treatments

- Anti-emetics are permitted for the treatment of nausea and vomiting and may be administered prophylactically for recurrent events. Routine pre-medication with anti-emetics for all patients is not advised.

- Hydroxyurea (AML) is permitted to control white blood cell count $< 10 \times 10^9/L$ during screening until the start of Cycle 2. It can be started or stopped at any point during this period. With the exception of hydroxyurea, no other direct anti-leukaemia therapy is permitted once study treatment has begun. Detailed documentation of dose and frequency must be recorded in the eCRFs and medication diary.
- High-dose steroids (ALL and leukaemia of ambiguous lineage) is permitted to control white blood cell count $< 10 \times 10^9/L$ during screening and Cycle 1 up to 4 days (maximum dexamethasone IV 40 mg/day or equivalent). It can be started or stopped at any point during this period. Detailed documentation of dose and frequency must be recorded in the eCRFs and medication diary.
- Low dose prednisone (10 mg or less) or equivalent dose of alternative steroid
- Intrathecal CNS prophylaxis may be continued.
- Supportive care, blood transfusions, and other medications that are considered necessary for the patient's wellbeing may be given at the discretion of the Investigator.
- Patients already receiving erythropoietin at the time of screening for the study may continue to receive it, provided they have been receiving it for > 1 month at the time study treatment is started. Prophylactic erythropoietin should not be started before Cycle 2.
- Granulocyte colony-stimulating factor (G-CSF) or granulocyte-macrophage colony-stimulating factor (GM-CSF) may be considered for prolonged neutropenia (> 7 days) and $< 5\%$ blast in bone marrow following discussion with the Medical Monitor ([Appendix F](#)). However, long-acting pegylated G-CSF (pegfilgrastim) or darbepoetin is not permitted.
- Patients may receive treatment with receptor activator of nuclear factor kappa-B ligand (RANKL) inhibitors and/or bisphosphonates for the treatment of osteopenia, as recommended according to practice guidelines.
- Allopurinol is mandatory prophylaxis for TLS, with dosing and schedule as per institutional guidelines. Rasburicase should be considered based on [Appendix F](#) and institutional guidelines.

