11.4.7.2 Dose-limiting Toxicity

Any event that meets the DLT criteria in the opinion of the Investigator should be reported to the Medical Monitor within 24 hours of knowledge of the event. Events will be assessed for DLT criteria according to the CTCAE National Cancer Institute (NCI) v5.0 (Section [8.3.2](#)) except for TLS, which will be assessed for DLT criteria using the Howard modification of Cairo-Bishop criteria ([Appendix G](#)). Toxicity that is clearly and directly related to the underlying malignancy or to an extraneous cause is excluded from the definition of a DLT. A DLT will be defined as the occurrence of any of the following:

- Any CTCAE Grade 3 non-haematological toxicity lasting > 7 days OR any CTCAE Grade 4 non-haematological toxicity, with the exception of:
 - CTCAE Grade 4 nausea, vomiting, or diarrhoea lasting < 7 days in the absence of maximum supportive therapy,
 - Elevation in serum amylase and/or lipase without clinical or radiographic evidence of pancreatitis,
 - CTCAE Grade 3 fatigue, asthenia, fever, anorexia, or constipation.
- Any other cardiac findings of CTCAE Grade ≥ 2 if considered by the Investigator to be clinically significant.
- AZD0466 should be permanently discontinued if a CTCAE Grade ≥ 3 cardiac AE of any duration occurs at any time during study treatment, if considered by the Investigator to be related to study treatment.
- AZD0466 should be permanently discontinued if liver function test abnormalities meets Hy's Law (HL) or Potential Hy's Law (PHL) criteria, and considered by the Investigator to be related to study treatment (see [Appendix E](#)).
- Prolonged myelosuppression: as myelosuppression and cytopenias are expected outcomes of leukaemia treatment, only the criteria defined below will be a DLT:
 - Lack of haematological recovery (ANC remaining $<0.5 \times 10^9/L$, platelets remaining $< 50 \times 10^9/L$) in the absence of active leukaemia in bone marrow (blasts $< 5\%$) and with marrow hypocellularity at $< 5\%$ by Day 42.
- Cairo-Bishop Grade ≥ 3 Clinical TLS ([Appendix G](#)) that occurs despite protocol-recommended management.
- Cairo-Bishop Laboratory TLS ([Appendix G](#)) with metabolic abnormalities that do not resolve within 5 days despite protocol-recommended management.
- Any other toxicity that
 - is greater than at baseline, is clinically significant and/or unacceptable, and is judged to be a DLT by the SRC, or
 - results in a disruption of dosing schedule of more than 21 days.

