- Any grade intracranial haemorrhage or haematoma

However, if there is evidence that the patient is experiencing clinical benefit with AZD0466, restarting at a reduced dose may be considered following discussion with the Medical Monitor. AZD0466 should be discontinued if significant bleeding reoccurs.

Anticoagulants and aspirin are not allowed during the study; other anti-aggregants may be used with caution.

F 2.2 Neutropenia and Febrile Neutropenia

The use of G-CSF (eg, filgrastim) or GM-CSF (eg, sargramostim) may be used for management of severe neutropenia or febrile neutropenia, according to institutional standards provided the patient has < 5% blasts in bone marrow and it is discussed with the Medical Monitor. The use of long-acting pegylated G-CSF (eg, pegfilgrastim) is not permitted during study treatment.

G-CSF or GM-CSF should not be administered within 72 hours prior to performing bone

marrow assessments.

F 2.3 Leucocyte Count

With the exception of hydroxyurea (AML) and high-dose steroids (ALL and leukaemia of ambiguous lineage) during screening and Cycle 1 up to 4 days (maximum dexamethasone IV 40 mg/day or equivalent), no other direct anti-leukaemia therapy is permitted once study treatment has begun. Both medications are to be used for white blood cell count control and can be started or stopped any point during this period.

F 2.4 Anaemia

Patients already receiving erythropoietin at screening may continue to receive it during study treatment, provided they have been receiving erythropoietin for > 1 month at the time study treatment is started.

Prophylaxis in Cycle 1: Prophylactic erythropoietin should not be started during Cycle 1.

Prophylaxis in cycle 2 and beyond: Prophylactic erythropoietin may be started during Cycle 2 or in subsequent cycles.

Use of the long-acting erythropoiesis-stimulating agent, darbepoetin, is not permitted during study treatment.

Blood transfusions may be administered at the discretion of the Investigator.

F 3 Guidance for Management of Fungal Infection

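### Three passages set different conditions for growth factor, and the prolonged-myelosuppression DLT is stated in two places that do not match on transfused platelets or marrow cellularity

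*Protocol*

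**What the plan says.** **Growth factor.** Three places in the protocol govern G-CSF/GM-CSF.

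- Table 5 in 6.6.1, for Grade 4 neutropenia occurring before remission: "Administer prophylactic or treatment anti-infectives and growth factor support as clinically indicated". No blast limit, duration or Medical Monitor step is attached to growth factor in that row.
- Section 6.5.1: G-CSF or GM-CSF "may be considered for prolonged neutropenia (> 7 days) and $< 5\%$ blast in bone marrow following discussion with the Medical Monitor".
- Appendix F 2.2: use for severe or febrile neutropenia "provided the patient has < 5% blasts in bone marrow and it is discussed with the Medical Monitor". No minimum duration is given.

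**Haematological DLT.** Two places state it.

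- Section 6.6.2 lets the next cycle start once ANC and platelets exceed their cut-offs "without platelet or growth factor support". Table 6 in that section is titled "Treatment Criteria Based on Bone Marrow, ANC and Transfusion Independent Platelet Count in the Absence of Peripheral Blasts". Its Cycle 1 row for low counts, blasts below 5% and cellularity below 10% provides for a repeat marrow at Day 42 and then says: "Blasts count < 5% and no count recovery this is prolonged myelosuppression and a DLT".
- Section 11.4.7.2 defines the same DLT as "Lack of haematological recovery (ANC remaining" below 0.5 × 10⁹/L and platelets remaining below 50 × 10⁹/L, with blasts below 5% and marrow cellularity below 5% by Day 42. It does not mention transfusion or growth factor.

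SAP 4.14.2 takes its DLT definition from 11.4.7.2 alone. The protocol's DLT section, for its part, sends the reader to Table 6 for the Day 42 myelosuppression assessment.

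**The concern.** The Table 5 row includes patients with 5% or more marrow blasts, whom 6.5.1 and F 2.2 exclude from growth factor. Two sites following the protocol in good faith could manage the same patient differently.

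The second difference reaches a primary endpoint. DLT and MTD are primary endpoints of Module 1 Part A, and DLT counts drive the mTPI-2 decisions. Platelet transfusion is permitted (6.5.1, F 2.1) and thrombocytopenia is named an important potential risk (2.2), so a transfused platelet count at Day 42 is a realistic case. If the two DLT statements classify that patient differently, both the dose decision and the reported DLT rate depend on which section was read.

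**Working it through.** No sample-size or power figure is involved. The check compares the passages and then reads the consequence from Table 10.

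**1. Conditions for growth factor**

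| Source | Neutropenia duration | Marrow blasts | Medical Monitor |
|---|---|---|---|
| Table 5, before remission | none stated | none stated | none stated |
| 6.5.1 | > 7 days | < 5% | discussion required |
| F 2.2 | none stated | < 5% | discussion required |

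All three differ. Table 5 conflicts with both others for a patient with 5% or more blasts. Sections 6.5.1 and F 2.2 conflict with each other for a patient with under 5% blasts whose neutropenia has lasted 7 days or less.

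**2. Conditions for the prolonged-myelosuppression DLT**

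| Element | Table 6, Cycle 1 row | 11.4.7.2 |
|---|---|---|
| ANC | < 0.5 × 10⁹/L | < 0.5 × 10⁹/L |
| Platelets | < 50 × 10⁹/L, transfusion independent (title) | < 50 × 10⁹/L, silent on transfusion |
| Blasts | < 5% | < 5% |
| Cellularity | < 10% (row entry) | < 5% |
| Growth-factor-supported ANC | not addressed | not addressed |

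**3. Two patients who separate the definitions** (both without circulating blasts, as the Table 6 title requires)

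- *Transfused platelets.* Day 42, blasts < 5%, cellularity < 5%, ANC 0.3, platelets 60 after transfusion and below 50 without it (× 10⁹/L). Table 6: the transfusion-independent platelet count is not recovered, so this is a DLT. Section 11.4.7.2 with both counts required: 60 is not below 50, so it is not. If 11.4.7.2 were read as needing only one low count, ANC 0.3 would make it a DLT under both.
- *Cellularity.* Both counts low without support, blasts < 5%, cellularity between 5% and 10%. Table 6: DLT. Section 11.4.7.2: not a DLT. This case needs no assumption about transfusion or lineage.

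In both cases Table 6 gives the DLT and 11.4.7.2 does not, so the definition cited by the SAP yields the lower count.

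**4. Effect of one reclassified patient, read from Table 10**

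| Patients | Fewer DLTs | One more DLT |
|---|---|---|
| 3 | 0: escalate | 1: stay |
| 3 | 1: stay | 2: de-escalate |
| 5 | 1: escalate | 2: de-escalate |
| 6 | 1: escalate | 2: stay |
| 6 | 2: stay | 3: de-escalate |

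Not every cell changes: at 6 patients, 0 and 1 DLT both give escalate.

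**The case against.** *The growth-factor passages can be read together.* Section 6.6.1 refers supportive therapy to Appendix F, and Table 5 is headed as a recommendation. Patients not yet in remission may also have fewer than 5% blasts. The last point stands: the row is not the same as active leukaemia. But the Appendix F pointer sits in a sentence about withholding dosing in subsequent cycles, Table 5 does not repeat the blast condition, and the pointer leaves the difference between 6.5.1 and F 2.2 in place.

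*The DLT passages are specification against silence.* This is fair for transfusion, and 11.4.7.2 is not free-standing, since the Day 42 extension refers to Table 6. It does not answer the cellularity cut-offs, which are two different numbers.

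*A reader might infer that Table 6 also rejects a growth-factor-supported ANC.* The documents do not support that. The Table 6 title qualifies platelets only, and the phrase excluding growth factor support appears only in the next-cycle sentence of 6.6.2, not in the DLT bullet. F 2.2 bars growth factor within 72 hours before a marrow assessment, but no passage says how a supported ANC counts towards the DLT.

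*A reader might infer that one unrecovered lineage suffices, because 11.4.7.2 joins ANC and platelets with a comma.* This is thin. The hold criterion in 6.6.2 joins them with a conjunction and the Table 6 rows pair low ANC with low platelets. Mixed cases go to the Medical Monitor. The point merits one clarifying word, not a finding of contradiction.

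*The Table 10 changes are generic.* True: any DLT ambiguity produces them. The SRC may also declare other toxicities DLTs, which can settle individual cases but supplies no uniform definition.

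**Conclusion.** The point holds on two counts. The three growth-factor passages set different conditions. The prolonged-myelosuppression DLT has two statements that differ on platelet transfusion and on cellularity (below 10% against below 5%). The transfusion example assumes that 11.4.7.2 requires both counts to be low, as the parallel passages suggest; the cellularity example does not need this.

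One reclassified patient can change a Table 10 decision at cohort sizes of 3, 5 and 6. How often that would happen cannot be estimated from the documents, and nothing in them shows that any actual decision was affected. Permission to transfuse is itself consistent across sections; only the reading of a transfused count differs.

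Severity is should-fix. A reader might call it essential because a primary endpoint is involved. However, SAP section 1 records that recruitment stopped on 16 June 2023 and that the study was terminated, and SAP 4.14.3 places the MTD evaluation outside this analysis. What remains live is the DLT tabulation in SAP 4.14.2.

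**What to change.** - Reconcile Table 5, 6.5.1 and F 2.2 so that one stated condition governs G-CSF/GM-CSF.
- State the DLT in 11.4.7.2 and Table 6 in the same words, covering four items: a platelet count under transfusion, an ANC under growth factor, whether both lineages or either must fail, and the cellularity cut-off.
- In SAP 4.14.2 and the CSR, say which definition was applied to the tabulated DLTs and identify any patient whose classification would differ under the other.
- Confirm that transfusion dates were recorded. Section 6.5 requires dates for medications and vaccines but does not name transfusions, and SAP 4.10 does not mention them.

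Which growth-factor rule and which DLT criteria apply is for the sponsor's clinical team. The cost is a wording clarification and a sentence or footnote in the SAP and CSR. If transfusion dates were not captured, the affected patients would need a source-data check.
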